**The primary study objective is:**

1) To determine the feasibility (enrollment, retention, data completion, satisfaction) of a 6-month behavioural and educational intervention to promote healthy behaviours for obesity prevention among young adults.

The **secondary objectives are:**

2) To determine the effects of the 6-month behavioural and educational intervention, compared to an educational intervention only, on change in BMI, health behaviours (nutrition, physical activity and sedentary time), health-related quality of life, and mental health (depression and anxiety).

3) To explore whether obesity risk stratification tools identify young adults who may be more successful in an obesity intervention.

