study office once a month to conduct a self weigh-in using a Fitbit electronic ‘smart’ scale (e-scale). They will be asked to weigh themselves monthly and reminders will be sent by email or text message. E-scales are feasible and valid for research conducted remotely and participant adherence to home weigh-ins is high(37–39), as part of this feasibility study we will assess the adherence to self weigh-ins when the scale is located in a private study office. Other secondary outcomes will include nutrition risk, physical activity (measured as 24-hour movement, including sedentary time and sleep), and mental health collected using online questionnaires at baseline and every 2 months. Nutrition risk will be measured using the National Cancer Institute's Dietary Screener Questionnaire (DSQ). The DSQ measures the frequency of intake of selected foods that are known to affect risk of cancer and obesity, including fruits, vegetables, whole grains, and sugary drinks. The DSQ has good validity compared to 24-hour recalls.(40) Self-reported physical activity, sedentary time, recreational screen time and sleep will be measured to describe adherence to recommended 24-hour movement guidelines using questionnaires previously used in young adults(41), including the International Physical Activity Questionnaire (IPAQ)(42), and International Sedentary Assessment Tool (ISAT).(43) The Insomnia Severity Index will also be included as a measure of perceived sleep quality.(44) Mental health is an important upstream determinant of health behaviours and is highly associated with obesity risk. We will measure depressive symptoms, anxiety and health-related quality of Life using the following validated tools: Centre for Epidemiologic Studies Depression Measure -10 (CESD-10)(45), Generalized Anxiety Disorder -7 (GAD-7)(46), and Euroqol-5D-5L (EQ-5D-5L).(47) We anticipate that some youth may also raise issues related to alcohol or substance use in the interviews, thus we have included questions that ask about alcohol, smoking, cannabis and medication use in the questionnaires. A single-item measure of body satisfaction is included in the study to evaluate any changes over the course of the study.(48) A validated two-item food insecurity screen is also included.(49)

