#### ***Data collection and management***

All data will be stored in a secure REDCap database. Surveys will be collected online using secure electronic data capture in REDcap. The final trial dataset will only be available to select members of the research team (LA, LM, TI). The final dataset will not be made publicly available to protect the confidentiality of participants, but de-identified data could be made available upon request. Baseline surveys will collect detailed data on socioeconomic variables, including age, sex, gender identity, income, and food security, medical history, and the secondary outcomes described above (nutrition, physical activity, sedentary time, mental health). Follow-up surveys administered every 2 months (at 2, 4 and 6 months) will collect updated data on secondary outcomes. Participants in both the control and intervention groups will receive a \$30 gift card at the time of each survey completion. We will continue to collect data from participants if they deviate from protocol unless there is withdrawal from the study. To ensure confidentiality, a unique study id number will be used for the weight and activity data and linked at McMaster by the research team to the main study database.

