#### ***Safety protocols and unanticipated outcomes***

Possible adverse outcomes may include concerns related to mental health, including eating disorders, or frustration due to weight gain/no change. Expectations of the research will be laid out before enrollment and feelings such as these can be addressed as part of the motivational interviewing process. Our research team including the research assistants/interviewers and physician co-investigator (EA) are equipped to assess the situation and provide necessary referrals. Medical and counselling services are available on campus for all

students. If participants raise any concerns of self-harm or harm to others, then safety protocols will be followed.

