### ***Data Analysis***

The analysis and reporting of our results will be done according to the CONSORT guidelines.(51) The data analyst will be blinded. Patient screening, randomization, allocation, and follow-up numbers will be illustrated in a flow diagram. Baseline data will be reported in a table for both groups (Intervention and Control) and summarised as means (standard deviation) or median (first quartile, third quartile) for continuous variables and counts (percent) for categorical variables. Data on feasibility outcomes will be measured and compared to pre-determined thresholds for interpretation. The primary analysis will be by intention-to-treat (data from participants will be analyzed according to their allocation irrespective of whether they received that intervention). For these purposes, a complete data set is required. Multiple imputation techniques will be used to manage missing data points. Comparison of groups for secondary outcomes will be reported descriptively for this pilot study. No formal significance testing for comparisons of the secondary clinical outcomes will be made because this is a pilot study with *a priori* sample size determined based on feasibility outcomes only. It is well established that there are sex and gender differences in obesity.(52) Disaggregated data on sex and gender will be reported.

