### ***Sample size***

Our sample size estimation was based on feasibility considerations and calculated using WINPEPI.(53) Using a 95% confidence level, assuming that 80% of the participants will complete the study with a 7.5% margin of error, 110 participants are needed (55 intervention and 55 control). This sample size is not sufficiently powered to make between-group comparisons but will provide accurate data on feasibility and estimates of effect size variability that will inform the sample size calculation of a larger definitive trial.

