**Table 1. Summary of all outcome measures and method of analysis**

Outcome measure	Variable Type	Measurement	Method of analysis
Primary Feasibility Outcomes			
Recruitment rate	Binary	% of eligible participants who are recruited from all those who contact the research team to learn about the study	Feasibility threshold of ≥50%

Retention rate	Binary	% of participants who complete 6-month follow-up	Feasibility threshold of $\geq 80\%$ .
Data completion	Binary	% of secondary outcomes with no missing data	Feasibility threshold of $\geq 80\%$ .
Satisfaction	Continuous	Mean score on a 7-point Likert scale	Mean satisfaction score $\geq 4$
Secondary Outcomes			
BMI change	Continuous	Change in BMI from baseline to 6-month follow-up, weight measures using wifi enabled smart scales	Mean, SD
Physical activity	Binary	International Physical Activity Questionnaire (IPAQ)	Mean, SD
	Continuous	Minutes per day from activity trackers	Mean, SD
Sedentary time	Binary	International Sedentary Assessment Tool (ISAT)	Mean, SD
Nutrition	Continuous	National Cancer Institute's Dietary Screener Questionnaire (DSQ)	Mean, SD
Mental health	Binary	Depressive symptoms (CESD-10) score $>10$ , Anxiety (GAD-7) score $>10$ ,	N, %
Health-related quality of life	Continuous	Quality of Life (EQ-5D-5L)	Median, IQR

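### Table 1 plans only the number and percent above 10 on CESD-10 and GAD-7, so no follow-up score, mean change or SD of change is reported for depression and anxiety

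*Combined protocol and SAP*

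**What the plan says.** Objective 2 (end of the Background) is to determine effects "on change in BMI, health behaviours (nutrition, physical activity and sedentary time), health-related quality of life, and mental health (depression and anxiety".

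Measurement of Outcomes names the instruments: "We will measure depressive symptoms, anxiety and health-related quality of Life using the following validated tools", namely CESD-10, GAD-7 and EQ-5D-5L. Questionnaires are given at baseline, and Data collection and management adds: "Follow-up surveys administered every 2 months (at 2, 4 and 6 months) will collect updated data on secondary outcomes".

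Measurement of Outcomes presents Table 1 as covering every outcome. Its mental health row has variable type binary, measurement "Depressive symptoms (CESD-10) score $>10$ , Anxiety (GAD-7) score $>10", and number and percent as the method of analysis.

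Data Analysis states: "Comparison of groups for secondary outcomes will be reported descriptively for this pilot study". It excludes formal testing of the secondary outcomes. For missing data it states: "Multiple imputation techniques will be used to manage missing data points". It also gives a rule for the baseline table: mean (SD) or median (quartiles) for continuous variables, and counts for categorical ones.

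The Sample size section says the pilot will provide "estimates of effect size variability that will inform the sample size calculation of a larger definitive trial". It names no outcome there.

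**The concern.** Objective 2 is about change. For depression and anxiety, the planned output is the percentage above a cut-off in each arm. That is a legitimate descriptive comparison and would show a net rise or fall. It does not show how far scores moved, how much they vary, or how much individuals changed.

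Two things are at stake. A reader of the pilot report would learn less about depression and anxiety than the data allow. And anyone considering either score as an outcome of the larger trial would not find in the planned report the SD at follow-up, the SD of change, or the baseline-to-follow-up correlation needed to size it.

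**Working it through.** **The plan's own figure.** The Sample size section uses 95% confidence, 80% completion and a 7.5% margin: n = z²p(1−p)/d² = 1.95996² × 0.80 × 0.20 / 0.075² = 109.27, rounded up to 110. This reproduces the stated figure. It concerns the precision of retention, involves no score SD, and is not affected by this point.

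**Table 1, secondary rows compared.**
- BMI change: mean, SD, and explicitly a change measure.
- Physical activity (questionnaire and tracker), sedentary time, nutrition: mean, SD.
- Quality of life: median, IQR.
- Mental health: number and percent above 10.

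Mental health is the only secondary row with no measure of spread. Two cautions apply. The type column is not fully reliable, since the IPAQ and ISAT rows are labelled binary but summarised by mean and SD. Also, the mental health measurement cell ends in a comma in the extracted text, so an item may have been lost. The reading does not depend on the type label alone: the threshold definition and the number-and-percent method agree with it.

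**Other places that could supply the summary.** The mean (SD) rule in Data Analysis applies to baseline data. It may produce a baseline SD if the scores are treated as continuous there. It does not produce a follow-up score, a change or an SD of change.

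**Illustrations.** The documents give no score distribution for either instrument. Everything below assumes normal scores with equal SDs, and the shares above the cut-off, means, 2-point difference and correlations are also assumed.

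1. *The SD cannot be recovered from a percentage.* Take 30% above the cut-off (z = 0.5244) and treat a score above 10 on an integer scale as above 10.5. Then SD = (10.5 − mean)/0.5244, which is 6.67 for a mean of 7 and 4.77 for a mean of 8. To detect 2 points with 80% power at two-sided 5%, n per arm = 2 × (1.960 + 0.842)² × SD²/2² = 175 or 90.
2. *Information kept by the cut.* For a small shift in mean, the relative efficiency is φ(z)²/[p(1−p)]: 0.490, 0.576 and 0.622 at p = 0.2, 0.3 and 0.4.
3. *Correlation.* With baseline adjustment, the required n scales with 1 − r²: 0.91 at r = 0.3 and 0.51 at r = 0.7, a ratio of 0.91/0.51 = 1.78. Percentages by visit do not give r. Visit SDs and the SD of change in the same participants do: r = (S₀² + S₁² − S_d²)/(2S₀S₁).
4. *Offsetting.* Of 44 completers in an arm (0.80 × 55), 13 above the cut-off at both times fits anything from 0 to 13 new cases. This is a counting limit, not evidence that it will happen.

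**What the pilot could report instead.** The 95% limits for a pooled SD are the estimate times √(df/χ²). With 88 completers (df 86) the factors are 0.870 to 1.175; with all 110 (df 108) they are 0.883 to 1.154.

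**The case against.** The strongest reply is that this is a pilot with descriptive secondary outcomes, that clinical cut-offs are meaningful, and that nothing is lost because the scores stay in the study database and the team can compute any SD later. Much of that stands. The data are not lost, a baseline SD may be reported, and percentages supply p(1−p), the variance needed to size a later trial on a binary endpoint. The gap is in what the plan commits to report at follow-up.

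It is also fair that unstated change is not special to this row. Only the BMI row specifies change, and the quality-of-life row gives no SD either. What sets mental health apart is that the score itself is not summarised at all.

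The illustrations are open to challenge too. A normal distribution with mean 7 and SD 6.67 puts about 15% of participants below zero (7/6.67 = 1.05 SDs), which is implausible if scores cannot be negative. They show the kind of information missing, not its amount.

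A reader might infer that the plan breaks its statement about effect size variability. The documents do not support that: the statement names no outcome and is met for BMI change. A reader might also infer a safety gap, because the protocol says "Possible adverse outcomes may include concerns related to mental health, including eating disorders, or frustration due to weight gain/no change". But those concerns are handled individually, through the interviews, referral and safety protocols, not through group scores, and the two scales do not count eating disorders.

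**Conclusion.** The point holds as a minor reporting gap. For depression and anxiety, the plan specifies a summary that discards collected score information and leaves the change element of Objective 2 undescribed, although a better summary is available from the same surveys.

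It does not follow that planners of the larger trial would have no SD at all: a baseline SD may be published, and the raw scores are retained. Nor is the decision to proceed at risk, because Measurement of Outcomes and Reporting and interpretation tie it to the feasibility outcomes only.

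The reading of Table 1 rests on the documents. Any figure for information loss or later sample size rests on assumed distributions.

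**What to change.** Keep the number and percent above 10. Add to the Table 1 mental health row, by arm and for each instrument:
- score, mean (SD), at baseline and at 2, 4 and 6 months;
- change from baseline, mean (SD), at 2, 4 and 6 months;
- the number observed for each, and median (IQR) as well if the scores are skewed.

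If the planned multiple imputation is applied to these outcomes, impute the score and derive the above-cut-off status from it, so that both summaries come from the same values.

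Optionally, add a small by-arm table of baseline against follow-up status on observed data. Label it descriptive, and note that crossings near the cut-off may be small fluctuations and that counts will be low.

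The cost is a few descriptive lines. It needs no new data, staff, participants or testing, and the sample size stays at 110. The resulting SDs will be rough planning figures only.
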